5.6 Duration of Follow Up

After completion of protocol therapy or removal from protocol therapy, participants will be followed for 3 years, or until death, whichever occurs first. Follow-up studies should be done annually at 12, 24, and 36 months after therapy (see Table 2 for scheduled tests).

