8 STUDY CALENDAR

Baseline laboratory tests are to be conducted within 14 days prior to start of protocol therapy. Other evaluations (scans, pathology, EKG, etc.) must be done within 30 days of study entry. In the event that the participant's condition is deteriorating, laboratory evaluations should be repeated within 48 hours prior to initiation of the next cycle of therapy.

All assessments must be performed prior to administration of any study medication. All study assessments and medications should be administered within ± 3 days of the protocol-specified date, unless otherwise noted.

All follow-up assessments must be performed 12, 24, and 36 months from the off-treatment date (i.e. Day 28 of last administered cycle) ± 31 days.

A calendar for the time points when the required study data should be obtained is provided below.

CONFIDENTIAL

This document is confidential. Do not disclose or use except as authorized.

Table 2: Required Data / Study Calendar

Assessments	Baseline/ Screening (within 14 days)	Before Starting Each Cycle (within 3 days)	During Each Cycle	End of Cycle 2 ⁵	End of Treatment (+/- 7 days from day 28 of Cycle 6)	Follow- up ⁷ (+/- 31 days)
Informed Consent	X ¹					
Medical History Concurrent Condition Concomitant Medications/ Transfusions	X					
Height		X			X	
Weight		X			X	
BSA		X			X	
Physical exam/Vital Signs	X	X			X	
Performance Status	X ¹	X			X	
Hematology (CBC/Diff/Plts)	X ¹	X	Weekly ⁴		X	X ²
Electrolytes including Ca ⁺⁺ , PO ₄ , Mg ⁺⁺	X	X	Weekly ⁴		X	X ²
Creatinine, BUN, Serum glucose	X ¹	X	Weekly ⁴		X	X ²
LFTs (Total Protein/Alb., ALT, AST, ALP, Billi.)	X ¹	X	Weekly ⁴		X	X ²
Uric acid	X	X ²			X ²	
Serum β-HCG ³	X ¹				X	
EKG	X				X ²	
Urinalysis	X	X			X	
Bone Marrow Biopsy, Aspirate and Smear	X ² (within 30 days)			X ²	X ²	X ²
Disease Assessment/ Response Documentation (CT/MRI/ Bone Scan/ PET, as clinically indicated)	X ¹ (within 30 days)			X	X ⁶	X ⁸
Chest X-Ray PA and L	X				X	
Skeletal survey (stratum 1 only)	X			X	X ⁶	X ⁸
Clofarabine Administration			Days 1-5			
Adverse Event Assessment	X	X	Weekly ⁴		X	

¹ Source documents are required for eligibility review before registration.

² As clinically indicated.

³ For females of childbearing potential.

⁴ Weekly assessments are recommended as clinically indicated, to be completed every 7 days, +/- 3 days.

⁵ End of Cycle 2 assessments must be completed on Day 28 of Cycle 2 +/- 7 days, and prior to starting Cycle 3.

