⁶ End of treatment disease assessment imaging window +/- 14 days from day 28 of Cycle 6.

⁷ All Follow-Up Assessments to be performed 12, 24, and 36 months from the off-treatment date (i.e. Day 28 of last administered cycle) +/- 31 days.

⁸ 12, 24, and 36 months after completion of therapy (i.e. Day 28 of last administered cycle)

CONFIDENTIAL

This document is confidential. Do not disclose or use except as authorized.

9 CRITERIA FOR RESPONSE – STRATUM 1

In contrast to leukemia or other malignancies the terms “remission” or “relapse” should be avoided. In accordance with the nature of Histiocytosis the following definitions should be applied to judge the effect of treatment. The response criteria stated below has been designed by the Histiocyte Society to be applied in therapeutic studies of LCH and should be used for therapeutic decisions.⁶⁸

Table 3: Definition of Disease State

Main Category	Sub-categories	Definition
Non-active Disease (NAD)		Resolution of all signs/symptoms (no evidence of disease)
Active Disease (AD)	Regressive Disease (Better)	Regression of signs/symptoms, and no new lesions.
	Stable Disease (Stable)	Persistence of signs or symptoms, and no new lesions.
	Progressive Disease* (Worse)	Progression of signs/symptoms and/or appearance of new lesions.

* Progression of skeletal lesions is defined as unequivocal enlargement of the size of existing lesions and/or appearance of new lesions.

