13.3 Study Design/Endpoints

The primary endpoint within each stratum will be the proportion of responders. A responder is defined as an eligible, evaluable participant who achieves either complete resolution or regression of disease, i.e., their disease gets "Better" per section 9.1, as the best overall response at any time up to and including the End of Cycle 2 assessment, which must be completed on Day 28 of Cycle 2 +/- 7 days, and must be completed prior to starting Cycle 3.

Secondary endpoints are:

- a) Progression-free survival (PFS), where time to event for PFS is the time from study enrollment until the time of first occurrence of new lesions, progressive disease, or death from any cause, or until last contact if no event occurs;
- b) Overall survival (OS), calculated as the time from enrollment until death or last contact;

CONFIDENTIAL

This document is confidential. Do not disclose or use except as authorized.

- c) Feasibility, which is assessed by the proportion of patients who experience a toxicity-event. Participants who have clofarabine stopped because of toxicity concerns will be considered to have experienced a toxicity-event. Otherwise, participants who complete therapy or who are removed from protocol therapy for reasons related to disease progression, second malignancy or death unrelated to protocol therapy will be considered to have successfully tolerated treatment; and,
- d) The proportion of participants reporting grades 3-4 toxicity, for each CTCAE v4.0 toxicity code.

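### PFS is censored at last contact rather than at last documented disease status, so late PFS can be overstated if patients are in contact without being assessed

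*Combined protocol and SAP*

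**What the plan says.** Section 13.3 counts PFS from enrolment "until the time of first occurrence of new lesions, progressive disease, or death from any cause", "or until last contact if no event occurs". The next item defines overall survival, "calculated as the time from enrollment until death or last contact", so the two endpoints share one censoring date. Neither section 13.4 (Evaluability) nor section 13.6 (Statistical Methods) ties PFS censoring to a disease assessment or says how to treat a missed one. Section 13.6 reports Kaplan-Meier PFS by stratum and overall.

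The follow-up schedule is yearly. Section 5.6 states: "Follow-up studies should be done annually at 12, 24, and 36 months after therapy". Section 8 allows 31 days either side. The follow-up disease row in Table 2 reads "Disease Assessment/ Response Documentation (CT/MRI/ Bone Scan/ PET, as clinically indicated". The row below it schedules a skeletal survey at the same yearly visits, for Stratum 1 only.

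The section 9 criteria differ by stratum. In Stratum 1 (Table 3), progression can be declared on signs and symptoms or on new lesions. In Stratum 2 (section 9.2), the criteria rest on PET, CT or MRI and on bone marrow findings.

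**The concern.** Any contact shows whether a patient is alive. It shows whether the disease has progressed only if someone assessed the disease. Using last contact for both endpoints treats time in contact without an assessment as observed progression-free time. Such patients stay in the Kaplan-Meier risk set and cannot contribute a silent progression as an event, so the curve is pushed upward.

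Three situations could separate contact from assessment in this trial: a missed yearly assessment, a contact between yearly visits, and a visit at which imaging was judged not indicated. The last matters most in Stratum 2, which has no mandatory follow-up imaging although its progression criteria depend on imaging. With a 31-day window, a patient can be in contact about 13 months after the last on-time assessment, and longer if a yearly assessment is skipped.

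PFS belongs to secondary objective 1.4.a. There is no control arm in which the same bias would cancel, so any upward error goes directly into the reported estimate.

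**Working it through.** The documents state no PFS rate, event count or precision, so there is no figure to reproduce. The size below is an illustration under stated assumptions.

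**Inputs from the documents.** Assessments fall at the end of Cycle 2 (day 56), the end of Cycle 6 (day 168), and 12, 24 and 36 months later. With 30.44 days per month, these are months 1.8, 5.5, 17.5, 29.5 and 41.5 from the start of treatment, taken as enrolment.

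**Assumptions.** Progression times are exponential. Every patient stays in contact to month 41.5. The three yearly assessments are each missed with probability m.

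**Formula.** Under last-contact censoring nobody leaves the risk set early, so reported PFS at month 41.5 equals true PFS plus the probability of having progressed undetected. Write S2 to S5 for true PFS at months 5.5, 17.5, 29.5 and 41.5. If misses are intermittent and independent:

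excess = m(S4 − S5) + m²(S3 − S4) + m³(S2 − S3)

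**Scenario 1: 18-month median.** S2 = 0.8085, S3 = 0.5093, S4 = 0.3209, S5 = 0.2021.
- m = 20%: 0.2 × 0.1188 + 0.04 × 0.1884 + 0.008 × 0.2992 = 0.034, so reported PFS is 23.6% against a true 20.2%.
- m = 30%: 0.3 × 0.1188 + 0.09 × 0.1884 + 0.027 × 0.2992 = 0.061, giving 26.3%.

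**Scenario 2: true PFS 67% at month 41.5.** S2 = 0.948, S3 = 0.845, S4 = 0.752, S5 = 0.670. The excess is as follows.

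| Missed per visit | Intermittent | Intermittent, half of progressions found clinically |
|---|---|---|
| 0% | 0 | 0 |
| 10% | 0.9 points | 0.5 points |
| 20% | 2.1 points | 1.0 point |
| 30% | 3.6 points | 1.8 points |

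The last column is half the one before it, because only silent progressions can be missed. In scenario 1 at m = 20%, the same step gives 20.2 + 3.4/2 = 21.9% with half found clinically, and 20.2 + 0.2 × 3.4 = 20.9% with 80% found clinically.

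**Persistent non-assessment.** If a patient once missed stays unassessed but in contact:

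excess = [1 − (1 − m)³](S4 − S5) + [1 − (1 − m)²](S3 − S4) + m(S2 − S3)

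At a true PFS of 67% and m = 20%, this is 0.488 × 0.082 + 0.36 × 0.093 + 0.2 × 0.103 = 0.094, so 67% is reported as about 76%. At m = 10% it is about 72%.

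**The alternative censoring date.** Simulation of 60,000 patients per scenario agrees with the figures above. It also gives the Kaplan-Meier estimate when event-free patients are censored at the last completed yearly assessment:
- No progression found clinically, scenario 1: 19.8% at 20% missed and 19.2% at 30% missed, against a true 20.2%.
- No progression found clinically, true 67%, persistent misses of 20%: 66.9%.
- Half found clinically and still counted as events, true 67%, 20% persistently un-imaged, censoring at last imaging only: about 61%. Last-contact censoring gives about 72% in the same scenario.

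The last result shows that an imaging-only rule can err by more (about 6 points down) than the present rule (about 5 points up). Symptomatic patients supply events after their last scan, while event-free patients are cut back to theirs.

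**The case against.** The strongest reply is that the protocol does not plan for contact without assessment. Patients without progression have no separate survival-contact schedule. Their follow-up contacts are the 12-, 24- and 36-month visits, disease assessment falls at those same visits, and section 8 makes it obligatory. The reduced follow-up in section 5.7 is for patients who have already progressed and so already have a PFS event. This stands: if the schedule is followed, the two censoring dates coincide.

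It is also true that an un-imaged patient is not necessarily an unassessed one. In Table 2 the clinical qualifier attaches to the imaging modalities, while the disease-assessment row itself is scheduled. Stratum 1 has an unqualified yearly skeletal survey, and its progression can be called on symptoms. A reader might infer that disease status goes largely unchecked in follow-up; the documents do not support that. The reply is weaker for Stratum 2, which has imaging-based criteria and no mandatory modality.

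Finally, the illustrated bias is small beside sampling error. With 25 patients the standard error is about √(0.202 × 0.798/25) = 8 points at a PFS of 20%, and √(0.67 × 0.33/25) = 9 points at 67%. That limits the consequence. It does not justify a rule whose error, when assessments of silent disease are missed, runs in one direction.

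**Conclusion.** The point holds conditionally. Section 13.3 as worded counts unassessed time as progression-free whenever a patient is in contact without a disease assessment, and nothing elsewhere in the plan corrects this. The direction is upward. The size is zero with complete yearly assessments and about 0 to 6 points with 10 to 30% missed intermittently. It is smaller when progression is recognised clinically, and larger (about 5 to 9 points at a true PFS of 67% with 10 to 20% missed per visit) if patients remain in contact but permanently stop being assessed. These sizes rest on assumed exponential progression and assumed missed-assessment rates; the documents give neither.

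A reader might infer that late PFS in this trial will be overstated. The documents do not support that, because scheduled contacts and assessments coincide and the rate of missed assessments is unknown. Nor does the point reach the primary analysis: PFS is descriptive, and the response test and both stopping rules do not use it. Yearly visits also date silent progression up to about a year late under either censoring rule; that is a separate matter, which this change does not address.

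**What to change.** In section 13.3, censor event-free patients for PFS at the last date on which disease status was documented as non-progressive under section 9, by clinical evaluation or imaging. Do not restrict this to imaging, because symptomatic progressions between visits count as events and imaging-only censoring would then bias PFS downward. Since the section 9.2 criteria are imaging- and marrow-based, say explicitly what counts as documented non-progression in Stratum 2. Keep last contact as the censoring date for overall survival, and report PFS censored at last contact as a sensitivity analysis.

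The cost is a short change of wording, somewhat shorter censored times and one extra descriptive analysis. No new visits are needed, because the assessments are already in Table 2. One limit remains: where a clinical evaluation is accepted without imaging, a silent progression can still go unseen. The new rule removes credit for contacts with no documented disease status, but not that residual error.

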1.4 Secondary Objectives

- a) To estimate the progression-free survival and overall survival of participants with recurrent or refractory LCH to clofarabine.
- b) To determine if clofarabine therapy can be delivered as planned ('chemotherapy feasibility'), and to describe toxicities of clofarabine in participants with LCH.
- c) To describe the toxicities and responses to clofarabine treatment in participants with LCH-related disorders.

CONFIDENTIAL

This document is confidential. Do not disclose or use except as authorized.

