5 TREATMENT PLAN

Each patient can receive a maximum of 6 cycles of study treatment. Each treatment cycle will last 4 weeks (28 days) and a delay up to day 42 is allowed if necessary to meet eligibility criteria for starting subsequent cycles. Patients will be stratified into two groups for response analysis purposes:

Table 1: Treatment Plan for all Patients

INDUCTION			MAINTENANCE			
Cycle						
1	2		3	4	5	6
Clofarabine 25 mg/m ² /day Days 1-5 I.V. 2 hrs +/- 30 min		Disease Evaluation	Clofarabine 25 mg/m ² /day Days 1-5 I.V. 2 hrs +/- 30 min			

Induction: Clofarabine on Days 1-5 of each cycle, administered as I.V. infusion at 25 mg/m²/day. No drug treatment from Day 6 to Day 28. This cycle will be repeated once.

Evaluation of disease response (see Section 9) will be performed after 2 cycles of Induction Therapy. In the absence of disease progression, participants will be eligible to receive up to 4 cycles of Maintenance Therapy, which is identical to the Induction Therapy.

Maintenance: Clofarabine on Days 1-5 of each cycle, administered as I.V. infusion at 25 mg/m²/day. No drug treatment from Day 6 to Day 28. Cycle will be repeated for up to three more times every 28 days.

CONFIDENTIAL

This document is confidential. Do not disclose or use except as authorized.

Treatment may be administered on an outpatient basis. Expected toxicities and potential risks as well as dose modifications for clofarabine is described in Section 6. No investigational or commercial agents or therapies other than those described below may be administered with the intent to treat the participant's malignancy.

5.1 Criteria to Proceed with Cycle 1

The following assessment must be completed within 3 days prior to starting Cycle 1. **Patients need to re-meet lab eligibility criteria as described in section 3.1.**

1. Complete physical examination including height, weight and BSA.
2. Performance status $\geq 70\%$ (use Lansky score for age < 16 and Karnofsky score for age ≥ 16 , see Appendix I).
3. Concurrent medical conditions.
4. Hematology: CBC with differential and platelet count and peripheral blood smear.
5. Serum chemistries: Electrolytes (calcium, magnesium, phosphorus, sodium, potassium, chloride, and bicarbonate), blood urea nitrogen (BUN), creatinine, and serum glucose. Liver function tests (total protein/albumin, aspartate aminotransferase (AST), alanine aminotransferase (ALT), alkaline phosphatase (ALP), total bilirubin).
6. Uric Acid as clinically indicated.

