6.3 Dose Modifications/Delays

6.3.1 Hematologic Toxicity

- Participants who experience prolonged neutropenia ($ANC < 500/\mu L$ for > 7 days) may receive growth factor support (see 5.3.7). If neutropenia persists ($ANC < 500/\mu L$) despite the addition of growth factor support and in the absence of hematopoietic involvement by Histiocytosis, but recovered by day 42 of the cycle, the subsequent cycle may start at a reduced dose of clofarabine by 25%. If prolonged neutropenia ($ANC < 500/\mu L$ for > 7 days) recurs in subsequent cycles after dose reduction, the participant should come off protocol treatment.
- Participants who experience prolonged thrombocytopenia (platelets $< 75,000/\mu L$ for > 7 days) in the absence of hematopoietic involvement by Histiocytosis should have their dose of clofarabine reduced by 25% in subsequent cycles. If prolonged thrombocytopenia (platelets $< 75,000/\mu L$ for > 7 days) recurs in subsequent cycles, the participant should come off protocol treatment.
- If ANC or platelets counts are not recovered by day 42 in the absence of hematopoietic involvement by Histiocytosis, the participant should be taken off study.

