Rule B – Three-stage stopping rule for toxicity events

Stage 1: Accrue 7 evaluable participants. If at any time 2 or more participants experience a toxicity-event, enrollment will be suspended for DSMB review of dosage modifications or stopping the trial. If 1 or fewer have a toxicity-event, then proceed to stage 2.

Stage 2: Accrue an additional 8 evaluable participants for a total of 15. If at any time 3 or more participants experience a toxicity-event, enrollment will be suspended for DSMB review of dosage modifications or stopping the trial. If 2 or fewer have a toxicity-event, then proceed to stage 3.

Stage 3: Accrue an additional 10 evaluable participants for a total of 25. If 7 or more participants experience a toxicity-event, then there is insufficient evidence to support chemotherapy feasibility. If 6 or fewer have a toxicity-event, then there is sufficient evidence that the therapy can be delivered as planned, and this evidence supports continuation until the accrual goal for this trial is reached.

If all 25 participants are evaluated and the true toxicity-event rate is 5%, the therapy will be considered tolerable with a probability of 0.94. If all 25 participants are evaluated and true toxicity-event rate is 30%, the therapy will be considered tolerable with a probability of 0.1.

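### Rule B concludes that clofarabine can be delivered as planned, but it counts only toxicity stops, and no summary of reductions, delays or dose delivered is planned

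*Combined protocol and SAP*

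**What the plan says.** The objective (Section 1.4.b) is "To determine if clofarabine therapy can be delivered as planned". Section 13.3.c turns this into an endpoint: "Feasibility, which is assessed by the proportion of patients who experience a toxicity-event". The event itself is defined in the next sentence: "Participants who have clofarabine stopped because of toxicity concerns will be considered to have experienced a toxicity-event". The success side follows: "Otherwise, participants who complete therapy or who are removed from protocol therapy for reasons related to disease progression", second malignancy or unrelated death are all regarded as having tolerated treatment. Completing therapy carries no condition on dose or timing.

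Rule B Stage 3 in Section 13.5 draws the conclusion: "If 6 or fewer have a toxicity-event, then there is sufficient evidence that the therapy can be delivered as planned".

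The treatment sections allow departures from the nominal schedule that do not end treatment. Section 6.3.1 says that after persistent neutropenia that recovers in time "the subsequent cycle may start at a reduced dose of clofarabine by 25"%, and it calls for the same reduction after prolonged thrombocytopenia. Section 5 says "a delay up to day 42 is allowed if necessary to meet eligibility criteria for starting subsequent cycles", and Section 5.2 repeats the 42-day limit. Section 6.3.2 provides for holding drug.

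For Objective 1.4.b, Section 13.6 plans Rule B and a table of grade 3 and higher toxicity by code. It plans nothing on dose.

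**The concern.** The question is about delivery, but the quantity counted is discontinuation for toxicity. A regimen can have few toxicity stops and still be given at a lower dose, or at longer intervals, in many participants. Followed to the letter, the plan would then report that the schedule is deliverable, and no planned table would show otherwise. The toxicity table counts each participant once per code at maximum grade, so it cannot show how long a cytopenia lasted, how often it recurred, or what it did to the next dose.

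The statement matters because Rule A decides whether clofarabine warrants further investigation. A feasibility claim reported beside that decision would be taken to describe 25 mg/m² on five days every 28 days. Section 13 itself describes the treatment as one standard dose and uses that to pool the strata for toxicity monitoring.

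**Working it through.** **1. Rule B's own figures.** Inputs from Section 13.5: at Stage 1, "Accrue 7 evaluable participants. If at any time 2 or more participants experience a toxicity-event", enrolment is suspended. At Stage 2 (15 cumulative) suspension comes at 3 or more events. At Stage 3 (25 cumulative) therapy passes with 6 or fewer. Treating a suspension as not passing,

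P(pass) = Σ Bin(x₁; 7, p) · Bin(x₂; 8, p) · Bin(x₃; 10, p), over x₁ ≤ 1, x₁+x₂ ≤ 2, x₁+x₂+x₃ ≤ 6.

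| True event rate p | Past Stage 1 | Past Stage 2 | Pass | Plan states |
|---|---|---|---|---|
| 5% | 0.956 | 0.937 | 0.937 | 0.94 |
| 30% | 0.329 | 0.109 | 0.096 | 0.1 |

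The plan's figures reproduce. The only unknown in the formula is p, the toxicity-event rate. Reductions and delays do not enter it, so no amount of either changes the pass probability.

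**2. Dose delivered by participants who count as successes.** Inputs from Sections 5 and 6.3.1: 25 × 5 = 125 mg/m² per cycle; 6 cycles = 750 mg/m² in 6 × 28 = 168 days; a reduced cycle is 0.75 × 125 = 93.75 mg/m²; maximum cycle length 42 days. I assume a single 25% reduction, since the text does not say whether two can be combined.

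Relative dose intensity (RDI) = (dose given / 750) × (168 / days taken).

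| Six-cycle course | Dose, mg/m² | Days | RDI |
|---|---|---|---|
| Reduced from Cycle 2, no delay | 125 + 5 × 93.75 = 593.75 | 168 | 0.79 |
| No reduction, 35-day cycles | 750 | 210 | 0.80 |
| No reduction, 42-day cycles | 750 | 252 | 0.67 |
| Reduced from Cycle 2, one 14-day delay | 593.75 | 182 | 0.73 |
| Reduced from Cycle 2, 35-day cycles | 593.75 | 210 | 0.63 |
| Reduced from Cycle 2, 42-day cycles | 593.75 | 252 | 0.53 |

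If the last cycle is counted as 28 days, the third row becomes 0.71 (238 days) and the last becomes 0.56. A single reduced, fully delayed cycle has 0.75 × 28/42 = 0.50. Every row is a success under Section 13.3.c, provided that clofarabine is not stopped for toxicity.

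**3. Up to the primary response assessment.** With a reduction and a full delay before Cycle 2: 218.75/250 = 0.875 of the dose over 42 + 28 = 70 days instead of 56, so RDI = 0.875 × 56/70 = 0.70.

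**4. The second definition.** Just before Rule B, Section 13.5 defines unacceptable toxicity as grade 5 events plus drug-related grade 3 or 4 non-hematological events with listed exceptions. Nothing connects this to the toxicity-event of Section 13.3.c that Rule B counts. If it were the intended event, non-fatal hematologic toxicity would still be outside it, and that is what triggers the Section 6.3.1 reductions. The gap remains under either definition.

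**5. Early leavers.** Someone who progresses after one or two cycles is also a success under Section 13.3.c, although most of the six planned cycles were never attempted.

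**The case against.** The strongest reply is that the modifications are part of the plan. The delay is written into the treatment plan, the reduction is prespecified, six cycles is a maximum, and Section 13.3.c says outright how feasibility is assessed. On that reading, a participant who completes with permitted modifications was treated as planned. This is a tenable reading, and it is why the point concerns wording and reporting and is not a design failure. But the protocol never states it, and a reader of the result would naturally take the nominal dose and interval.

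A reader might also infer that all 25 participants could receive about half the planned intensity with no toxicity-event. The documents do not support that as a realistic size. Section 6.3.1 takes a participant off treatment if prolonged neutropenia or thrombocytopenia recurs after a reduction, and off study if counts have not recovered by day 42. These would ordinarily be toxicity stops, so Rule B would count them. Reaching 0.53–0.56 needs repeated delays that never meet those criteria, for example a neutrophil count between 500 and the 750/µL required to start a cycle, or slow non-hematologic recovery. Growth factor support (Section 5.4.7) narrows this further.

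It is also fair that some related information is captured. Laboratory abnormalities that delay a cycle are adverse events (Section 10.1), and grade 3 and higher hematologic toxicity will appear in the Section 13.6 table. That shows a cause of modifications, but not how many participants were modified or how much drug they received.

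**Conclusion.** The point holds in a limited form. Rule B's arithmetic is correct and it is usable as a safety stopping rule, but its Stage 3 conclusion goes beyond what it counts. Plausible modified courses deliver roughly 63–80% of planned intensity and are indistinguishable from full delivery. The 79% case needs only one reduction. The 67% case assumes maximum delay in every cycle, and 50–56% is the extreme. How many participants would fall in each group cannot be derived from the documents.

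This rests on reading a stop in Section 13.3.c as ending clofarabine. If a temporary hold also counted, holds would become events, but reductions and late cycle starts would still be missed. Objective 1.4.b is secondary, and no error rate or boundary is affected. It is a cheap improvement that changes what the trial can claim about feasibility.

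**What to change.** Keep Rule B, its boundaries and all dosing rules.

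- **Sections 13.3.c and 13.5:** state whether the toxicity-event and unacceptable toxicity are the same thing, and which one Rule B counts.
- **Section 13.5, Stage 3:** limit the conclusion to an acceptable toxicity-event rate, as defined after that reconciliation.
- **Sections 13.3.c and 13.6 (Objective 1.4.b):** add a descriptive delivery measure for all treated participants. It should give the proportion with any toxicity-related reduction, omitted dose or late cycle start (later than day 28 plus the general 3-day window of Section 8), the number of cycles delivered, and RDI through Cycle 2 and over the cycles actually started. Fix in advance how the last cycle's length is counted, since that alone moves the extreme case from 0.53 to 0.56.
- **Early leavers:** count participants who leave for progression or other non-toxicity reasons up to their last cycle started, and show them separately so that disease failure is not mixed with intolerance. Read RDI beside the toxicity-event count, because someone stopped after one full cycle would otherwise look fully dosed.
- Base any statement that therapy was delivered as planned on this measure.

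The cost is a few sentences and one table. Table 2 already lists BSA before each cycle and clofarabine administration on Days 1–5. The downside is that the feasibility statement may look less favourable.
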